2.1 Objectives and Endpoints/Estimands

Objectives	Endpoints
Primary	

 • To evaluate the effect of olpasiran administered subcutaneous (SC) every 12 weeks (Q12W) compared with placebo, on percent change from baseline in Lp(a) after 36 weeks of treatment 	
 • Percent change in Lp(a) from baseline at week 36
Primary Estimand	

The primary estimand consists of:
 
 • The target population, which is adults with atherosclerotic cardiovascular disease and elevated Lp(a) • The primary variable, which is percent change from baseline in Lp(a) at week 36 • The intercurrent events which are the discontinuation of investigational product and excluded medication(s) taken during study. For the primary estimand, the treatment effect will be estimated in subjects who are randomized and received at least 1 dose of investigational product regardless of the occurrence of these intercurrent events • The summary measure, which is the difference between olpasiran and placebo in the mean percent change from baseline in Lp(a) at week 36 • The treatments to be compared are each olpasiran group vs. placebo 
The primary estimand is the difference between each olpasiran group and placebo in the mean percent change from baseline in Lp(a) at week 36 in adults with atherosclerotic cardiovascular disease and with elevated Lp(a) who are randomized and received at least 1 dose of investigational product, regardless of discontinuation of investigational product and excluded medication(s) taken during the study.
	
Secondary	

 • To evaluate the effect of olpasiran administered SC Q12W compared with placebo, on percent change from baseline in: 
 – Lp(a) after 48 weeks of treatment 	
 • Percent change from baseline in: 
 – Lp(a) at week 48 – LDL-C at week 36 and week 48 – ApoB at week 36 and week 48

 – Low- density lipoprotein cholesterol (LDL-C) after 36 and 48 weeks of treatment – Apolipoprotein(B) (ApoB) after 36 and 48 weeks of treatment 	

 • To characterize the pharmacokinetic (PK) properties of olpasiran 	
 • PK parameters for olpasiran including, but not limited to, maximum observed concentration (C_{max}), and the area under the concentration time curve (AUC)

Estimands for Secondary Endpoints

The estimands for the secondary endpoints in Lp(a), LDL-C, and ApoB are the differences between each olpasiran group and placebo in the mean percent change from baseline in:

- Lp(a) at week 48
- LDL-C at week 36
- LDL-C at week 48
- ApoB at week 36
- ApoB at week 48

For adults with atherosclerotic cardiovascular disease and elevated Lp(a) who are randomized and received at least 1 dose of investigational product, regardless of discontinuation of investigational product and excluded medication(s) taken during the study.

Exploratory

 • To evaluate the effect of olpasiran administered SC Q12W compared with placebo, on: 
 – percent change from baseline in Lp(a) – percent change from baseline in LDL-C – percent change from baseline in ApoB – achievement of Lp(a) < 125 nmol/L – achievement of Lp(a) < 100 nmol/L – achievement of Lp(a) < 75 nmol/L – achievement of Lp(a) < 50 nmol/L 	
 • Percent change from baseline at each scheduled visit, except weeks 36 and 48, in: 
 – Lp(a) – LDL-C – ApoB • Achievement at each scheduled visit of the following: 
 – Lp(a) < 125 nmol/L – Lp(a) < 100 nmol/L – Lp(a) < 75 nmol/L – Lp(a) < 50 nmol/L

 • To evaluate the effect of olpasiran administered SC Q24W compared with olpasiran administered SC Q12W and placebo, on: 
 – percent change from baseline in Lp(a) – percent change from baseline in LDL-C – percent change from baseline in ApoB – achievement of Lp(a) < 125 nmol/L 	
For the olpasiran SC Q24W group:
 
 • Percent change from baseline at each scheduled visit, in: 
 – Lp(a) – LDL-C – ApoB • Achievement at each scheduled visit of the following:

 - achievement of Lp(a) < 100 nmol/L - achievement of Lp(a) < 75 nmol/L - achievement of Lp(a) < 50 nmol/L 	
 - Lp(a) < 125 nmol/L - Lp(a) < 100 nmol/L - Lp(a) < 75 nmol/L - Lp(a) < 50 nmol/L
--	--

Objectives	Endpoints
Exploratory	

 • To estimate cardiovascular event rates in subjects treated with olpasiran, including aggregated exploratory analyses across the olpasiran program 	
 • Adjudicated events 
 - Death by any cause - Cardiovascular death - Myocardial infarction - Hospitalization for unstable angina - Coronary revascularization - Stroke - Transient ischemic attack - Cerebrovascular revascularization - Acute limb ischemia - Major amputation, or urgent peripheral revascularization for ischemia

 • To describe the effect of olpasiran of quality of life (QoL) measures as assessed using the PROMIS Global Health 	
 • Change from baseline in PROMIS Global Health measures at each scheduled visit

 • To evaluate the effect of olpasiran administered SC on inflammatory biomarkers 	
 • Change from baseline at week 48 in: 
 - high sensitivity (hs) C-reactive protein (CRP) - hs-Interleukin 6 (IL-6)

 • To assess the anti-olpasiran antibody response 	
 • Anti-olpasiran antibody formation, if tested
Safety	

 • To evaluate the safety and tolerability of olpasiran administered SC compared with placebo in subjects with elevated Lp(a) 	
 • Treatment emergent adverse events • Clinically significant safety laboratory values and vital signs at each scheduled visit

2.2 Hypotheses and/or Estimations

The null hypothesis is that there is no difference between olpasiran and placebo in percent change from baseline in Lp(a) at week 36 in subjects with atherosclerotic cardiovascular disease and with elevated Lp(a).

3. Study Overview

3.1 Study Design

This is a phase 2, double-blind, randomized, placebo-controlled, multicenter, dose finding study to evaluate efficacy, safety, and tolerability of olpasiran on Lp(a) compared to placebo in subjects with atherosclerotic cardiovascular disease and with elevated Lp(a).

Subjects will be randomized in a 1:1:1:1:1 ratio to 1 of the following 5 treatment groups (some olpasiran arms will include placebo to maintain blind):

- Group 1: 10 mg Q12W
- Group 2: 75 mg Q12W
- Group 3: 225 mg Q12W
- Group 4: 225 mg Q24W
- Group 5: Placebo Q12W

The randomization will be stratified by screening Lp(a) ≤ 200 vs. > 200 nmol/L and by region (Japan vs. Non-Japan).

The study treatment period is 48 weeks with doses at day 1, week 12, week 24, and week 36. After week 48 there is an extended safety follow-up without further dosing with investigational product for **a minimum of 24 weeks**. Subjects will remain on standard of care (including stable lipid-lowering therapy) per their local guidelines during the treatment period and extended safety follow-up period.

An administrative interim analysis will be performed when approximately 240 subjects have had the opportunity to complete the week 24 assessments or have early terminated. At that point, approximately 120 subjects may have had the opportunity to complete the week 36 assessments or have early terminated.

The interim analysis results will be used to support dose selection for a phase 3 registrational study and trigger early planning for the phase 3 program. In addition, the safety and efficacy results may be used in company internal discussions and external interactions with regulatory agencies. The study continues regardless of the administrative interim results.

Team members that remain directly involved with the conduct of the study, investigators and subjects will not receive results of the interim analysis and will remain blinded.

The primary analysis will occur when all randomized subjects have had the opportunity to complete the week 36 assessments or have early terminated. The end of treatment period analysis will occur when all subjects have had the opportunity to complete the week 48 assessments or have early terminated. Final analysis will occur after the last subject either completes the extended safety follow-up and has ended the study or has early terminated from the study.

The overall study design is described by a study schema in Section 1.2. in the protocol. The endpoints are defined in Section 2.1.

3.2 Sample Size

Assuming standard deviation of 30% as observed in phase 1 study, a 5% drop-out rate and with Bonferroni multiplicity adjustment to control family-wise type 1 error rate at 0.05, at least 48 subjects per arm provides at least 90% power to detect a treatment difference of 25% between an active and placebo arm in mean percent change of Lp(a) from baseline. It is expected to have 99% power to detect a treatment effect of -80% vs. -3% between active and placebo arms in mean percent change of Lp(a) from baseline. Considering 5% drop-out rate, at least 48 subjects per arm (at least 192 subjects in the 4 active treatment arms) provides a 95% confidence of detecting 1 case of an adverse event at an incidence of 1/60.

Up to a total of approximately 290 subjects may be enrolled.

3.3 Adaptive Design

Not applicable.

4. Covariates and Subgroups

4.1 Planned Covariates

Baseline covariates include, but are not limited to:

- Stratification factors
 - Screening Lp(a) (≤ 200 nmol/L vs. >200 nmol/L)
 - Region (Japan vs. Non-Japan)
- Age
- Sex
- Race
- Baseline Lp(a)

- Baseline LDL-C
- Baseline ApoB
- Baseline non-HDL-C
- Lipid Lowering Therapy (high intensity, not high intensity)
- Region (North America, Europe and Australia, other (including Japan))
- Ethnicity (Hispanic vs. Non-Hispanic)

4.2 Subgroups

Subgroups include, but are not limited to the following:

- Stratification factors
 - Screening Lp(a) (≤ 200 nmol/L vs. >200 nmol/L)
 - Region (Japan vs. Non-Japan)
- Age (< 65 years, ≥ 65 years)
- Sex (male, female)
- Race (White, Black, Other)
- Baseline Lp(a) by median
- Baseline LDL-C by median
- Baseline ApoB by median
- Baseline non-HDL-C by median
- Lipid Lowering Therapy (high-intensity, not high-intensity, as defined in Appendix C)
- Region (North America, Europe and Australia, other (including Japan))
- Ethnicity (Hispanic vs. Non-Hispanic)

If number of subjects in one or more categories is too small (e.g. less than 10%), the subgroup categories may be combined.

5. Definitions

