Lp(a) > 150 nmol/L would result in a study population with a median Lp(a) of approximately 200 nmol/L and allows evaluation of the effectiveness and safety of olpasiran in subjects with very high Lp(a).

A recent Mendelian randomization study suggests that in individuals with very high baseline Lp(a) concentrations, reducing Lp(a) by 80% to 90% is expected to translate into a clinically meaningful reduction in the risk of cardiovascular events (Khan et al, 2017; Leebmann et al, 2013; Safarova et al, 2013, Burgess et al, 2018, Lamina et al, 2019, Madsen et al, 2020).

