dose response models will be selected based on the known pharmacology and Lp(a) reduction of Olpasiran from phase I trials. The second step (Mod-step) relies on parametric modeling or model averaging to find the “optimal” dose for confirmatory trials. MCP-Mod method is found more effective than pairwise comparison due to its ability to utilize all available data from the continuum of active doses and placebo to estimate a parametric dose response curve which allows for interpolation and extrapolation of effect across a range of doses (Dinko Rekić et al, 2015).

Covariate analyses of the primary endpoint will be performed. Baseline covariates listed in Section 4.1 in their original format, will be included one at a time, in the repeated measures model used in the primary analysis.

Subgroup analyses on the primary efficacy endpoint will be conducted using the subgroups specified in Section 4.2. Treatment effect differences among subgroups, which represent subgroup by treatment interactions, will be estimated and tested based on statistics from the subgroup repeated measures models.

For covariate and subgroup analyses, the data-derived stratification factors will be used.

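### Effect modification by continuous baseline values, including Lp(a), is tested only on two-way splits; a continuous interaction would recover some power and give estimates by Lp(a) level at little cost

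*SAP*

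**What the plan says.** SAP 4.2 lists "Baseline Lp(a) by median" and the same median cut for LDL-C, ApoB and non-HDL-C. Age is cut at 65 years. The list also carries the stratification factor, screening Lp(a) at or below versus above 200 nmol/L.

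SAP 9.5.1 states how differences in effect are examined: "Treatment effect differences among subgroups, which represent subgroup by treatment interactions, will be estimated and tested based on statistics from the subgroup repeated measures models".

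The same section plans a covariate analysis: "Baseline covariates listed in Section 4.1 in their original format, will be included one at a time, in the repeated measures model used in the". The model it refers to is the primary one, which contains treatment group, stratification factors, visit and treatment-by-visit. No term lets the treatment effect vary with a continuous covariate.

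Protocol 2.1 says of the entry cut-off (above 150 nmol/L) that it "would result in a study population with a median Lp(a) of approximately 200 nmol/L and allows evaluation of the effectiveness and safety of olpasiran". The people meant are described there as having very high Lp(a).

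Neither document gives an expected interaction size or a power for the subgroup tests.

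**The concern.** A two-way split discards the ordering within each half. A subject at 210 nmol/L and one at 400 nmol/L count as the same. If the effect varies smoothly with baseline, the interaction test on the split has less power than a test on the measured value.

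For Lp(a) there is a second point. With an expected median of about 200 nmol/L, the median split and the stratification split would largely divide the subjects in the same way. The two tests would then add little to each other, and neither looks inside the upper half.

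At stake is how much the trial can say about whether the effect depends on starting Lp(a), in a study meant to support dose selection for phase 3. A null result from a low-power split is weak evidence of a consistent effect.

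**Working it through.** **Inputs from the documents.** SAP 3.2: "Assuming standard deviation of 30% as observed in phase 1 study", 5% drop-out, Bonferroni at a family-wise 0.05, 48 per arm, 25-point difference. Protocol 4.2: about 58 per arm. Protocol 2.1: entry above 150 nmol/L, expected median about 200. Protocol 4.3: predicted share of subjects reaching at least 80% suppression by month 12 is 42% (10 mg), 94% (75 mg) and 98% (225 mg Q12W).

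**Assumptions.** One dose versus placebo at a single time point; two-sided 5% for the interaction test; effect linear in baseline or in log baseline. The shape of the Lp(a) distribution and the within-subject CV are not in the documents, so ranges are shown.

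**Step 1: the plan's own power figure.** With 48 × 0.95 = 45.6 per arm, SE = 30 × √(2/45.6) = 6.28 and 25/6.28 = 3.98. Bonferroni over four comparisons: Φ(3.98 − 2.50) = 93%. Over three: Φ(3.98 − 2.39) = 94%. The stated figure of at least 90% is reproduced.

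**Step 2: information kept by a median split.** The share is r² = corr(X, 1[X > median])², which does not depend on the SD or on n.
- Normal baseline: 2/π = 0.64.
- Skewed Lp(a), taken as 150 plus an exponential excess with median 50, effect linear in log Lp(a): 0.61 (by simulation of that distribution).

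Other shapes, for sensitivity: uniform 0.75; lognormal excess with sigma 0.6 to 1.0, log scale, 0.56 to 0.50. For age the cut is at 65, not at the median, so the share depends on where 65 falls and was not calculated.

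**Step 3: power after the split** = Φ(r × (1.96 + z_power) − 1.96).
- Continuous power 80%, normal: Φ(0.798 × 2.80 − 1.96) = 61%.
- Continuous power 80%, log-scale skewed: Φ(0.783 × 2.80 − 1.96) = 59%.
- Continuous power 50%: Φ(0.798 × 1.96 − 1.96) = 35% (normal) and Φ(0.783 × 1.96 − 1.96) = 34% (log-scale skewed).

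**Step 4: gain for small gradients.** With 58 per arm, the SE of the slope difference per SD of baseline is 30 × √(2/58) = 5.57. Counting both tails:
- 3 points per SD: 3/5.57 = 0.54, so about 8% power (continuous) versus 7% (split).
- 5 points per SD: 5/5.57 = 0.90, so about 15% versus 10% to 11%.
- 80% power for the continuous test needs 2.80 × 5.57 = 15.6 points per SD.

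**Step 5: which gradients are plausible.** Percent change cannot go below −100%, so at least 80% suppression means a 20-point band. Under the exponential shape the SD is 50/ln 2 = 72, the 10th percentile is about 158 and the 90th about 316: (316 − 158)/72 = 2.2 SD. A gradient of 15.6 points per SD would spread responses over 2.2 × 15.6 = 34 points, wider than the band predicted to hold 94% to 98% of subjects on 75 mg and 225 mg Q12W. A gradient of 5 gives 11 points, which fits. The 10 mg group, at 42%, leaves more room.

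**Step 6: precision of the split.** With about 55 evaluable per arm, the SE of the difference between the two halves is 30 × √(8/55) = 11.4. The difference detectable with 80% power is 2.80 × 11.4 = 32 points, more than the 25 points used to size the main comparison.

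**Step 7: overlap of the two Lp(a) splits.** Simulated with a median of 200 and an assumed within-subject CV of 15% down to 5%, the splits put about 83% to 95% of subjects on the same side. With a median of 220, 240 or 260, agreement falls to about 79% to 83%, 73% and 67%.

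**The case against.** The best case against has four parts.

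First, a reader might infer that the plan cannot show the effect at very high Lp(a). The documents do not support that. In Protocol 2.1 the phrase can be read as describing the whole enrolled population above 150 nmol/L, which the primary comparison addresses. The subgroup analyses add an average effect, with inference, above about 200. What is missing is an estimate by level, and no stated objective asks for one. This stands.

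Second, a reader might quote a heavier loss. If the effect were linear in raw nmol/L, the exponential shape keeps 48% of the information, and 80% power falls to 49%. That is not the log-scale model proposed here, for which the fall is to about 59%. Large absolute gains also need steep gradients that sit badly with the suppression predicted for the two higher Q12W doses. This also stands, with two limits: 10 mg leaves more room, and an active-arm SD well below 30 would raise power for both tests.

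Third, the overlap of the Lp(a) splits is a projection. One uses the screening value and the other the mean of the two most recent values, and the realised median may exceed 200. Reporting a stratification factor as a subgroup is ordinary practice. This is fair.

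Fourth, these are unpowered supportive analyses with no decision rule, both lists are open-ended, and a separate exposure-response analysis (Protocol 6.4.2.2) supports dose selection. That limits the consequence. It does not put a continuous interaction test into the plan, and whether the exposure-response plan models baseline Lp(a) cannot be seen from these documents.

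**Conclusion.** The point holds as a modest, inexpensive improvement. Effect modification by the continuous baselines is tested only on two-way splits, and no treatment-by-continuous-covariate term is specified. If the effect changes smoothly, the median split costs roughly 20 percentage points of power where a continuous test would have 80%, and about 15 where it would have 50%. Where the gradient is 5 points per SD or less, neither test has useful power and the gain is at most about 5 percentage points. The main benefit there is an estimate with a confidence interval by Lp(a) level.

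The figures rest on assumed distribution shapes, SD 30, 58 per arm and a smooth trend; a true step at the cut would lose nothing. The redundancy of the two Lp(a) splits holds only if the realised median is near 200 nmol/L. The primary result and its multiplicity control are not affected.

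**What to change.** In SAP 9.5.1, base the effect-modification test for baseline Lp(a), LDL-C, ApoB, non-HDL-C and age on the continuous value, using log baseline for Lp(a). Add baseline, baseline-by-visit, treatment-by-baseline and treatment-by-baseline-by-visit terms to the repeated measures model, one variable at a time. Report the week 36 treatment difference with 95% CI at fixed baseline Lp(a) percentiles, for example the 10th, 25th, 50th, 75th and 90th. Keep the two-category estimates as description and as a check on linearity.

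The cost is SAP wording and a few extra model runs on data already collected. The downside is that the test assumes a roughly linear trend in baseline (log baseline for Lp(a)).

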5.1 Study Time Points

Enrollment Date

The enrollment date for each subject is recorded on the Subject Enrollment eCRF.

Randomization Date

Randomization date is defined as the date subject was allocated to a treatment group in the interactive response technology (IRT) as recorded on the Subject Enrollment eCRF.

Study Day 1

For each subject, Study Day 1 is defined as the date of the first dose of investigational product (IP) administration.

Study Day

For each subject, and for a given date of interest, study day is defined as the number of days since Study Day 1:

Study Day = (date of interest – Study Day 1 date) + 1.

If the date of interest is prior to the Study Day 1:

Study Day = (date of interest – Study Day 1 date), so that the day prior to Study Day 1 is study day -1.

First Dose Date of Investigational Product

For each subject, the First Dose Date of Investigational Product is defined as the date of the first administration of IP as recorded on the Investigational Product Administration eCRF.

Last Dose Date of Investigational Product

For each subject, the Last Dose Date of Investigational Product is defined as the date of the last administration of IP as recorded on the Investigational Product Administration eCRF.

End of Treatment Period Date

For subjects who have week 48 assessment, the End of Treatment Period Date is the maximum date of all week 48 assessments. For subjects early withdraw study before week 48, the End of Treatment Period Date is the EOS date. ie. End of Treatment Period Date is defined as min (maximum date of all week 48 assessments, EOS date).

Extended Safety Follow-up Period Start Date

Extended Safety Follow-up Period Start Date = End of Treatment Period Date + 1

End of Investigational Product (EOIP) Date

End of Investigational Product Date is defined as the date of decision was made to end investigational product recorded on the End of Investigational Product Administration eCRF.

End of Study (EOS) Date for Individual Subject

End of Study is defined as the date subject ended study recorded on the End of Study eCRF.

Study End Date for the Overall Study

The Study End Date is the last EOS date of all randomized subjects.

5.2 Demographics and Baseline Related Definitions

Age

Age at randomization will be collected as the subject's age in years at enrollment as recorded on the Demographics eCRF.

Baseline Lipid and Lipid-related Parameters

Baseline values for Lp(a), lipids (total cholesterol, HDL-C, LDL-C, VLDL-C and triglycerides), ApoA1, ApoB, and their derived parameters (eg, ratio between them) are defined as the mean of the two most recent non-missing concentrations measured through central lab prior to or on study day 1. If for any reason only 1 value is available, then that value will be used as baseline.

Other Baseline Values

For all other variables, the baseline value is defined as the last non-missing value collected prior to or on Study Day 1.

BMI

Subject's BMI will be derived in kg/m² in the clinical database on the Physical Measurement eCRF.

Change (absolute change) from Baseline

The arithmetic difference between a post-baseline value and baseline for a given time point:

Change from baseline = (post-baseline value – baseline value)

Percent Change from Baseline

The percent change from baseline for a given variable at a given time point is defined as:

$$[(\text{value at a given post-baseline time point} - \text{baseline value}) / \text{baseline value}] \times 100\%$$

